### **2.4 Risks/Benefits**

Anticipated risks. No serious risks are anticipated with this study. Cardiopulmonary exercise testing (CPET) may cause some fatigue and physical discomfort. Psychological discomfort, such as anxiety or apprehension, may arise for participants related to undergoing MRI and CPET. These are not seen as significant risks with levels of discomfort beyond those that they might experience during situations

outside of the study. Participants will be informed that they can stop participating in the study at any time.

Risks associated with the intervention are minimal, even for individuals with reduced cardiorespiratory fitness. However, adverse events may occur with exercise:

*Exercise training.* The major risks of participating in this monitored program include muscle fatigue, muscle soreness, and possible joint or skeletal injury. These risks are reduced by enrolling women without contraindications to exercise modifications, proper warm-up/cool down periods, conservative exercise prescriptions and progression, and monitoring by experienced staff (including exercise physiology specialists). If experienced, exercise-related injuries are expected to be of minimal discomfort and short duration and not significantly different than what someone might experience in everyday physical activities.

The study will maintain ongoing compliance with all University of Washington guidelines surrounding COVID-19 mitigation for in-person clinical research.

All adverse events, regardless of attribution to study procedures, will be collected and recorded. Subjects will be asked in an open-ended way about the presence of any adverse events. The PI will comply with all requirements of the IRB for the reporting of safety data and adverse/serious adverse events. For more information, see the study Data & Safety Monitoring (DSM; Appendix A)

Storing all data with only a code attached will help ensure confidentiality. However, there is a potential risk of breach of confidentiality related to collection of sensitive information and participant identifiers. Following procedures outlined in Section 9.0 will minimize possible breaches of confidentiality and obtaining informed consent will limit invasion of privacy.

**MRI risk management.** Participants in our study will not receive gadolinium-based contrast agents for the MRI scans.

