### **3.0 STUDY AIMS**

1. Determine the feasibility of an individually-adaptive exercise intervention among breast cancer survivors with reduced cardiorespiratory fitness through examination of recruitment rate, enrollment rate, loss to follow-up, intervention adherence, and relative dose intensity (ratio of total completed to total planned cumulative dose)

2. Examine the endpoint of (a) safety; and explore the endpoints of (b) cardiorespiratory fitness; (c) functional capacity; (d) physiologic changes; and (e) patient reported outcomes (PRO) in the intervention vs control arms.
3. Examine the endpoint of (a) safety; and explore the endpoints of (b) cardiorespiratory fitness; (c) functional capacity; (d) physiologic changes; and (e) patient reported outcomes (PRO) in the AE vs RE vs AE+RE intervention arms.

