## 4.0 STUDY DESIGN

### 4.1 Description of Study

This is a pilot study of a 2-arm randomized trial with a 2:1 initial allocation to exercise intervention or waitlist control (see Appendix B for study schema). The intervention group will then be randomly assigned (1:1) to receive either a 12-week aerobic exercise (AE) intervention or a 12-week resistance exercise (RE) intervention.

At 12 weeks, the intervention group will be assessed for intervention response, defined as a  $\geq 5\%$  increase in 6-minute walk distance (6MWD) over baseline. Non-responders to either AE or RE will receive 12 weeks of combined AE+RE. Intervention responders will continue the exercise intervention in their current assignment, either AE or RE alone, for the additional 12 weeks.

This study will employ a waitlist control. After 24 weeks, the waitlist control group will receive a digital copy of sessions provided to the intervention arm. The control and intervention arms' schedule of evaluations will be identical across all 24 weeks of the trial.

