##### *Intervention Safety*

Safety: Intervention safety will be determined by reviewing and quantifying the number of adverse events (mild, moderate, or severe), serious adverse events, and by reviewing the type and severity of adverse events attributed to study procedures among each study group. See Section 8.0 for adverse event definitions and protocols.

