#### 4.3.5 Schedule of Evaluations

STUDY PROCEDURES	Baseline	Week 12	Week 24
Intervention Arm			
CPET	X		X
MRI	X		X
6MWT	X	X	X
1-RM	X	X	X
Anthropometrics	X	X	X
Questionnaires	X	X	X
Safety (ongoing)	X	X	X
Accelerometry (ongoing)	X	X	X
Control Arm			
CPET	X		X
MRI	X		X
6MWT	X	X	X
1-RM	X	X	X
Anthropometrics	X	X	X
Questionnaires	X	X	X
Safety (ongoing)	X	X	X
Accelerometry (ongoing)	X	X	X

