## 7.0 GUIDELINES FOR ADVERSE EVENT REPORTING

### 7.1 Adverse Event Reporting/Institutional Policy

In accordance with institutional policy, all adverse events which in the opinion of the principal investigator are unexpected and related or possibly related to the research and serious or suggest that the research places research participants or others at greater risk of physical or psychological harm than was previously known or recognized be reported to the IRB within 10 calendar days of learning of the problem.

Definitions:

**Adverse Event** - Any untoward medical occurrence in a participant, such as any unfavorable and unintended sign (including an abnormal laboratory finding, for example), symptom, or disease temporally associated with the intervention.

**Life-threatening Adverse Event** – Any adverse event that places the participant, in view of the investigator, at immediate risk of death from the reaction.

**Unexpected Adverse Event** – An adverse event is “unexpected” when its nature (specificity), severity, or frequency are not consistent with (a) the known or foreseeable risk of adverse events associated with the intervention; and are also not consistent with (b) the characteristics of the subject population being studied including the expected natural progression of any underlying disease, disorder or condition any predisposing risk factor profile for the adverse event.

**Serious Adverse Event (SAE)** – Any adverse event occurring that results in any of the following outcomes:

- death
- a life-threatening adverse event (real risk of dying)
- inpatient hospitalization or prolongation of existing hospitalization
- a persistent or significant disability/incapacity
- a congenital anomaly
- requires intervention to prevent permanent impairment or damage

**Attribution** - The following are definitions for determining whether an adverse event is related to a medical product, treatment or intervention procedure:

- An adverse event is **related or possibly related to the research procedures** if in the opinion of the principal investigator, it was more likely than not caused by the research procedures.

- Adverse events that are solely caused by an underlying disease, disorder or condition of the subject or by other circumstances unrelated to either the research or any underlying disease, disorder or condition of the subject are not “related or possibly related.”

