Next, the analysis will explore the impact of the intervention on the outcome of CRF in intervention participants versus waitlist control participants using generalized linear models (GLM) comparing baseline to 24-week measurements. This analysis will be repeated for the additional outcomes of functional capacity, i.e., submaximal exercise capacity; physiologic changes, i.e., thigh IMF:SM, abdominal depots of fat (VAT, SQ, RP, and IP fat), and body weight; and patient reported outcomes, i.e., QOL, perceived well-being, and fatigue. These analyses will be performed according to the intent-to-treat principle, where outcomes are analyzed by intervention assigned, regardless of the level of adherence. A secondary per protocol analysis will be conducted, and these results will be reported and interpreted together with the intent-to-treat analysis. This per protocol analysis will include only those participants who (a) completed all clinic visits and who completed at least 85% of the required physical activity. In addition, this secondary analysis will investigate factors related to a lack of intervention adherence, which will include baseline measures of perceived well-being, mood disturbance, perceptions of PA, fatigue, and insomnia.

For objective 3, the analysis will explore the impact of AE vs RE vs combined AE+RE on safety outcomes using generalized linear models (GLM) comparing pre-intervention measurements to post-intervention measurements. Next, this analysis will be repeated for the additional outcomes of CRF, functional capacity, physiologic changes, and patient reported outcomes of QOL, perceived well-being, and fatigue.

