### COLLECTION AND REPORTING OF SAEs AND AEs

For this study, the following standard AE definitions are used:

**Adverse event:** Any unfavorable and unintended sign (including an abnormal laboratory finding), symptom or disease temporally associated with the use of a medical treatment or intervention procedure, regardless of whether it is considered related to the medical treatment or intervention procedure.

**Serious Adverse Event:** Any AE that results in any of the following outcomes:

- Death
- Life-threatening
- Event requiring inpatient hospitalization or prolongation of existing hospitalization
- Persistent or significant disability/incapacity

AEs are graded according to the following scale:

**Mild:** An experience that is transient & requires no special treatment or intervention. The experience does not generally interfere with usual daily activities. This includes transient laboratory test alterations. A mild AE typically corresponds to a 1 on the NCI Common Terminology Criteria for Adverse Events (CTCAE).

**Moderate:** An experience that is alleviated with simple therapeutic treatments. The experience impacts usual daily activities. Includes laboratory test alterations indicating injury, but without long-term risk. A moderate AE corresponds to a 2 on the CTCAE.

**Severe:** An experience that requires therapeutic intervention. The experience interrupts usual daily activities. If hospitalization (or prolongation of hospitalization) is required for treatment it becomes an SAE. A severe AE corresponds to a 3 on the CTCAE.

The study uses the following AE attribution scale:

**Not related:** The AE is clearly not related to the study procedures (i.e., another cause of the event is most plausible and/or a clinically plausible temporal sequence is inconsistent with the onset of the event).

**Possibly related:** An event that follows a reasonable temporal sequence from the initiation of study procedures, but that could readily have been produced by a number of other factors.

**Related:** The AE is clearly related to the study procedures.

AEs are identified by participant self-report at each study follow up assessments (12-, 24-, 36- and 48-weeks). Participants will be asked about medical or mental health events that have happened since the previous assessment visit. AEs may also be identified during supervised (in-person or remote) exercise sessions, with an event either occurring or being reported during such sessions.

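### Objective 3 applies a pre/post GLM to adverse events, which suits them poorly, and does not settle how women who move to AE+RE are counted

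*Combined protocol and SAP*

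**What the plan says.** Aim 3 (Section 3.0) names safety first among the endpoints to be examined "in the AE vs RE vs AE+RE intervention arms". For that aim, Section 10.0 explores the effect of modality "on safety outcomes using generalized linear models (GLM) comparing pre-intervention measurements to post-intervention measurements", then repeats the same analysis for fitness, functional capacity, physiologic and patient-reported outcomes.

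Section 4.2.2 defines safety by numbers of adverse and serious adverse events and "by reviewing the type and severity of adverse events attributed to study procedures among each study group". Section 7.1 defines an adverse event as a sign, "symptom, or disease temporally associated with the intervention". Appendix A collects events at follow-up assessments: "Participants will be asked about medical or mental health events that have happened since the previous assessment visit". Section 2.4 adds that "Subjects will be asked in an open-ended way about the presence of any adverse events", and the schedule in Section 4.3.5 has a row opening "Safety (ongoing" that is ticked at baseline as well as at Weeks 12 and 24.

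The combined regimen arises in one way only (Section 4.1): "Non-responders to either AE or RE will receive 12 weeks of combined AE+RE". Responders stay on AE or RE alone for the second 12 weeks.

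**The concern.** A pre/post contrast needs the same quantity measured before and after. Peak oxygen consumption and walk distance meet that requirement. Adverse events, as this plan defines and collects them, do not: they accumulate after the intervention starts. The baseline tick comes with no instrument and no look-back window from which a pre-intervention count could be formed. The GLM's outcome distribution, link and any exposure term are also unstated for safety.

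The second gap is the grouping. AE+RE exists only in Weeks 13-24 and only in non-responders, each of whom has already spent 12 weeks on AE or RE. The plan does not say whether a switcher's events in Weeks 1-12 belong to her starting modality or to AE+RE, or whether unequal time at risk is allowed for. Under some choices, modality is confounded with calendar period and length of exposure, so a safety difference could appear where none exists. Section 2.2 presents the study as a first step toward testing one modality against another, so a reader will look at that comparison.

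**Working it through.** **No figure to reproduce.** The plan gives no number for this comparison, no expected response rate and no expected event rate.

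**Inputs from the documents.** 30 women (Section 4.3.1). Allocation is 2:1, so 30 × 2/3 = 20 intervention women, then 1:1, so 10 AE and 10 RE (Section 4.1). There are two periods of 12 weeks.

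**Assumptions.** Full follow-up; Week 12 response r = 30%, 50% or 70%, equal in AE and RE; event rates as stated in each step.

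**Step 1: person-weeks under three grouping rules.**
- Randomised assignment: AE = RE = 10 × 24 = 240; AE+RE = 0.
- Modality received: AE = RE = 10 × 12 + 10 × r × 12; AE+RE = 20 × (1 − r) × 12.
- Final modality: AE = RE = 10 × r × 24; AE+RE = 20 × (1 − r) × 24.

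| Response | Women moving to AE+RE | Received: AE and RE, each | Received: AE+RE | Final: AE and RE, each | Final: AE+RE |
|---|---|---|---|---|---|
| 30% | 14 | 156 | 168 | 72 | 336 |
| 50% | 10 | 180 | 120 | 120 | 240 |
| 70% | 6 | 204 | 72 | 168 | 144 |

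Under the final-modality rule, 12 of each AE+RE woman's 24 weeks (50%) were spent on a single modality.

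**Step 2: women with at least one event, modality received, equal true rate of 0.05 per week (assumed).** The chance is 1 − exp(−0.05 × weeks): 0.699 over 24 weeks and 0.451 over 12. AE and RE mix 24-week responders with 12-week switchers, so their proportion is r × 0.699 + (1 − r) × 0.451:
- r = 30%: 0.210 + 0.316 = 53%
- r = 50%: 0.349 + 0.226 = 57%
- r = 70%: 0.489 + 0.135 = 62%

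On AE+RE it is 45% throughout. The gap comes from exposure time alone.

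**Step 3: adjusting for person-time is not enough if risk changes over time.** Assume 0.05 per week in Weeks 1-12, 0.02 in Weeks 13-24, and no modality effect. Pool AE and RE by modality received:
- r = 30%: (240 × 0.05 + 72 × 0.02) / 312 = 13.44 / 312 = 0.0431; ratio 0.02 / 0.0431 = 0.46
- r = 50%: (240 × 0.05 + 120 × 0.02) / 360 = 14.40 / 360 = 0.0400; ratio 0.50
- r = 70%: (240 × 0.05 + 168 × 0.02) / 408 = 15.36 / 408 = 0.0376; ratio 0.53

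Under the final-modality rule every woman expects 12 × 0.05 + 12 × 0.02 = 0.84 events and the ratio is 1.0. The choice of rule alone moves the answer from 1.0 to about 0.5. Start-up effects are the plan's own expectation: Section 6.1 reduces early RE sessions because of soreness. Appendix D starts the added regimen at Level 1, so switchers may have a second start-up phase, which would push the ratio the other way. The direction of the distortion is therefore not predictable.

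**Step 4: splitting by period.** In Weeks 1-12, AE and RE are compared as randomised, 10 against 10 women, 120 person-weeks each. In Weeks 13-24 every woman contributes 12 weeks, with 3/3/14, 5/5/10 or 7/7/6 women on AE/RE/AE+RE. Under the Step 3 assumptions the Weeks 13-24 ratio is 0.02 / 0.02 = 1.0.

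**Step 5: precision.** With no events in n women, the exact two-sided 95% upper limit is 1 − 0.025^(1/n): 23% for n = 14, 31% for n = 10, 46% for n = 6. Only description is realistic.

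**The case against.** A reader might infer that the stated analysis cannot be run at all. The documents do not support that. Safety is ticked at baseline, and events are to be recorded whatever their attribution (Section 2.4). Asking about events since the previous visit also separates Weeks 1-12 from Weeks 13-24, so for a switcher one could improvise a count before and after AE+RE began. What stands is that the pre-intervention measure is undefined and the method suits the outcome poorly.

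It can also be said that Section 10.0 already fixes the grouping, since it analyses women according to the intervention assigned. But that sentence belongs to the Objective 2 paragraph. Read as randomised assignment, it leaves AE+RE with no women; and Section 2.2 describes the switch as a re-assignment, so the phrase could mean either thing. It does not settle the matter.

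Section 4.2.2 does define safety descriptively by study group, and Objective 2 already stratifies events by severity, seriousness and attribution. Neither says that group means modality, gives a denominator for modality, or deals with switchers.

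Two further limits stand. At 30% response the person-weeks are nearly equal (156 against 168). And setting 70% (24 weeks) against 45% (12 weeks) as the AE-or-RE versus AE+RE gap would overstate it, because AE and RE include switchers' 12-week exposure; the 53/57/62% figures allow for this.

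**Conclusion.** The point holds: the analysis stated for Objective 3 safety does not fit the outcome, and the counting of switchers is left open. Depending on the rule chosen, AE+RE exposure ranges from none, through 168/120/72 person-weeks, to 336/240/144 at 30/50/70% response. An as-treated pooled rate ratio near 0.5 can arise with no modality effect. These sizes rest on 20 intervention women, full follow-up, and response and event rates that the documents do not give.

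A reader might infer that the wrong modality would be carried into the later trial. The documents do not go that far: no passage makes Objective 3 safety a selection rule. The supported statement is that the description of safety by modality could mislead. The primary endpoint (intervention discontinuation) and the feasibility-and-safety judgement in Section 10.0 are not affected. In a 30-woman pilot this is minor to should-fix.

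**What to change.** In Section 10.0, take safety out of the Objective 3 pre/post GLM and replace it with a descriptive table by modality in force at event onset, split by period:

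- Weeks 1-12: AE against RE, as randomised.
- Weeks 13-24: AE, RE and AE+RE, with a note that these groups are not randomised and that AE+RE contains only Week 12 non-responders.

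In each cell give women with at least one event, number of events, person-weeks and events per person-week, broken down by severity, seriousness and attribution. Record the onset date of each event if the case report form does not already do so. The GLM can stay for outcomes that have a baseline measurement.

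The cost is one replaced sentence, one more descriptive table and possibly one form field. Sample size and visits do not change.

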#### 4.3.4 Data Collection

Clinical and self-report data will be collected at 3 total timepoints: baseline, 12 weeks, 24 weeks.

**Self-reported data:** Participants will be asked to complete baseline questionnaires ascertaining demographic information, health history and current health behaviors. At all timepoints (i.e. baseline, 12-, and 24-Week) participants will be asked to complete self-reported questionnaires on quality of life, physical activity, and fatigue.

**Clinic visits:** In-person clinic visits will take place at baseline and 24-weeks for all participants. All clinic visits will include anthropometric assessment, MRI, supervised 6MWT and CPET. Participants will complete a supervised 6MWT. Study procedures will occur at the University of Washington Medical Center and the Fred Hutchinson Prevention Center. At intervention completion participants will be asked open-ended questions regarding their experience with the study. The responses will be analyzed for themes to improve future study designs.

**Passive Data Collection:** Some data will be remotely collected via wrist- and waist-worn actigraphy monitors, worn in the 7 days prior to each clinic visit. Wrist-worn monitors will be worn 24 hours a day including sleep, while waist-worn monitor will be removed for sleep. Wrist-worn devices will also be utilized during all intervention sessions, as a measure of intervention adherence.

Measure	Type of measure	Instrument	Source
Sample Characteristics			
Demographics	Baseline	Questionnaire	Participant
Physical & mental health history	Baseline	Questionnaire	Participant
Intervention Feasibility			
Intervention Feasibility	Primary outcome	Attendance/Retention	Case Report Form
Intervention Acceptability	Secondary outcome	Questionnaire	Participant
Exercise intervention adherence	Other/Exploratory outcome	Actigraphy Monitor	Participant
Exercise intervention adherence	Secondary outcome	RPE	Participant
Intervention session Intensity	Secondary outcome	RPE	Participant
Safety			
Safety	Secondary outcome	Adverse Events	Case Report Form
Cardiorespiratory Fitness			
VO 2 (maximal exercise capacity)	Other/Exploratory outcome	CPET	Case Report Form
Functional Capacity			
6MWD (submaximal capacity)	Other/Exploratory outcome	6MWT	Case Report Form
1 Repetition Maximum (strength)	Exploratory outcome	1-RM	Case Report Form
Physiologic Changes			
Anthropometrics	Other/Exploratory outcome	Physical exam	Case Report Form

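### Objective 3 does not define the pre-measurement for AE+RE, and with CPET and MRI only at baseline and Week 24 the AE+RE period cannot be separated out for peak VO2 or MRI fat

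*Combined protocol and SAP*

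**What the plan says.** Aim 3 (section 3.0) lists safety, fitness, functional capacity, physiologic change and patient-reported outcomes ("PRO) in the AE vs RE vs AE+RE intervention arms"). Section 10.0 carries this into Objective 3: generalized linear models "comparing pre-intervention measurements to post-intervention measurements", first for safety, after which "this analysis will be repeated for the additional outcomes of CRF, functional capacity, physiologic changes, and patient reported outcomes". It does not say which visits are meant. For Objective 2 the same section names baseline and Week 24.

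Under section 4.1, "At 12 weeks, the intervention group will be assessed for intervention response", on a 5% rise in 6-minute walk distance (6MWD) over baseline. Then "Non-responders to either AE or RE will receive 12 weeks of combined AE+RE", while "Intervention responders will continue the exercise intervention in their current assignment, either AE or RE alone, for the additional 12 weeks".

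On measurement, section 4.3.4 (Data Collection) says "In-person clinic visits will take place at baseline and 24-weeks for all participants" and "All clinic visits will include anthropometric assessment, MRI, supervised 6MWT and CPET". The schedule in section 4.3.5 agrees for CPET and MRI: both are ticked at baseline and Week 24, with Week 12 empty in both arms. Section 4.2.3 takes cardiorespiratory fitness from peak VO2 at CPET, and thigh and abdominal fat from MRI.

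**The concern.** AE+RE exists only in the second half of the trial. A pre-to-post change for it needs a value at the point where it begins, and for CPET and MRI outcomes no such value is planned. Followed as written, the analysis can still yield a figure labelled AE+RE for peak VO2 or MRI fat, but that figure would describe a sequence: AE then AE+RE, or RE then AE+RE. Someone reading the pilot's results to judge the promise of combined training would credit or blame it for 12 weeks in which it was not given.

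**Working it through.** The plan states no figure for this comparison, so there is none to reproduce. The check sets the schedule against the analysis and then sizes the possible distortion under stated assumptions.

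**1. What the schedule (section 4.3.5) allows**

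| Outcome | Baseline | Week 12 | Week 24 | Week 12-24 change | Baseline-Week 24 change |
|---|---|---|---|---|---|
| CPET | yes | no | yes | no | yes |
| MRI | yes | no | yes | no | yes |
| 6MWD, 1-RM, anthropometrics, questionnaires | yes | yes | yes | yes | yes |

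For an AE+RE participant, baseline-to-Week-24 change = (12 weeks of AE or RE alone) + (12 weeks of AE+RE). The single-modality share of the time is 12/24 = 50%. Without a Week 12 value the two terms cannot be separated.

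**2. Group sizes.** From N = 30, 2:1 and then 1:1: 30 x 2/3 = 20 intervention, 10 starting AE and 10 starting RE. The documents give no non-response rate. If it is 20% to 70%, AE+RE has 20 x 0.2 = 4 to 20 x 0.7 = 14 women.

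**3. Timing alone, with no selection.** Let a and r be the mean Week 0-12 gains on AE and RE, s the share of AE+RE women who started on RE, c the second-period gain on AE+RE and b that on continued AE. Then

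AE+RE minus AE alone = [(1 - s)a + s r + c] - [a + b] = (c - b) + s(r - a).

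The term s(r - a) has nothing to do with AE+RE. Assume a = +2.0 and r = +0.5 mL/kg/min:

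- s = 0: 0
- s = 0.25: 0.25 x (-1.5) = -0.375
- s = 0.5: 0.5 x (-1.5) = -0.75
- s = 0.75: 0.75 x (-1.5) = -1.125
- s = 1: -1.5

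Against RE alone the corresponding term is (1 - s)(a - r), which is +0.75 at s = 0.5. It vanishes if AE and RE give equal first-period gains.

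**4. Selection on top.** Assume no difference between regimens in Weeks 12-24, bivariate normal 12-week changes in 6MWD and VO2 with correlation rho, and non-response of 30%, 50% or 70%. In a simulation of 1,000,000 draws per setting, the baseline-to-Week-24 contrast of AE+RE minus single modality, in SDs of the 12-week VO2 change, is:

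- rho = 0: about 0
- rho = 0.3: -0.48 to -0.50
- rho = 0.5: -0.80 to -0.83
- rho = 0.7: -1.12 to -1.16

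**The case against.** The strongest reply is that the intervention means the whole 24-week adaptive programme. The primary endpoint (section 4.2.1) counts stopping before Week 24, section 4.2.2 speaks of assessments after the intervention, and section 2.2 describes re-assignment as part of one intervention. On that reading the pre-measurement is baseline, and every participant has a planned CPET and MRI at both ends. This stands as a possible reading. A reader might therefore infer that the AE+RE change simply cannot be computed; the documents do not support that without qualification, because it is true only if the pre-measurement is Week 12. The baseline reading does not rescue the label, however: section 10.0 compares three modalities, and a baseline-to-Week-24 change belongs to a sequence. Appendix A calls the design SMART, which suggests comparing strategies, but Objective 3 does not name any.

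Three other strong readings also go too far.

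- **Sign reversal from timing.** One can assume first-period gains of +2.0 for responders and 0 for non-responders, then +0.5 and +1.5, giving 2.5 against 1.5 overall (-1.0) although AE+RE gained 1.0 more in the second period. That reversal comes from the assumed selection. If both groups start on AE and gain +1.0, then (1.0 + 1.5) - (1.0 + 0.5) = +1.0, the same as 1.5 - 0.5.
- **All fat measures affected.** Only MRI fat is; weight and circumferences are scheduled at Week 12.
- **The AE+RE figure will choose the modality for a larger trial.** No section says so. Section 10.0 makes feasibility and safety the main consideration and explores other outcomes only if those are favourable.

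**Conclusion.** The point holds in a limited form. For peak VO2, thigh fat-to-muscle ratio and abdominal MRI fat, no change specific to AE+RE can be separated out, whichever reading of the pre-measurement is intended. That follows from the documents alone. The size of any resulting distortion rests on assumptions: -0.75 mL/kg/min against AE alone for the assumed gains and an even split (0 to -1.5 over all splits), and zero if AE and RE act equally in the first 12 weeks. Selection can add roughly -0.5 to -1.2 SD for correlations of 0.3 to 0.7, and nothing at zero correlation.

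These are exploratory outcomes in a pilot. The primary endpoint and the Objective 2 comparison with control are unaffected. The correction is still worth making, since it is cheap and changes what may be claimed for combined training.

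**What to change.** In Aim 3 and Objective 3:

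1. Define the pre and post visits for each comparison, and state that an AE+RE-specific change in CPET and MRI outcomes is not estimable.
2. For those outcomes, compare baseline-to-Week-24 change by randomised starting modality, AE-first against RE-first (about 10 against 10). Show change by full sequence received as description only.
3. Limit any Week 12-24 change for AE+RE to the outcomes scheduled at Week 12: 6MWD, 1-RM, anthropometrics and questionnaires. Label it descriptive and non-randomised. For 6MWD add a warning about regression to the mean: Week 12 6MWD decides who enters AE+RE, so women with a chance-low walk are over-represented and their later gain is inflated, while responders' later gain is deflated.
4. Reconcile section 4.3.4 (Data Collection), which places in-person visits at baseline and Week 24 only, with the Week 12 measures in section 4.3.5. This matters most for 1-RM, which section 4.2.2 bases on chest and leg press machines.

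The cost is wording and table labels, with no added CPET or MRI. The downside is giving up an AE+RE-specific claim on fitness and MRI fat. The AE-first against RE-first contrast will be imprecise at this size, but it keeps the randomisation.
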